H1a: PTSD will be associated with increased systemic levels of IL-1b, TNF- α and IL-6. H1b: WTC workers with asthma and PTSD will have an increased expression of sputum neutrophilia and IL-6 levels. H1c: Increased sputum neutrophilia and higher IL-6 levels will be associated with poorer disease control among WTC workers with asthma.

2. Examine the longitudinal association between PTSD and symptom perception in WTC workers with asthma

H2a: WTC rescue and recovery workers with PTSD will be more likely to over-perceive asthma symptoms in naturalistic settings compared to participants without PTSD. H2b: Associations between subjective (Asthma Control Questionnaire, use of rescue medications, and Asthma Quality of Life Questionnaire scores) and objective (forced expiratory volume in 1 second [FEV₁]) measures of asthma control will be weaker among WTC workers with PTSD than those without PTSD.

3. Assess the relationship between PTSD and adherence to asthma SMB (medication adherence, trigger avoidance, and inhaler technique) in WTC workers and identify the pathways linking them

H3a: PTSD is associated with lower adherence to SMB among WTC workers with asthma. H3b: Asthma (identity, timeline, and cause), medication beliefs (necessity and concerns about controller medications), and over-perception of symptoms will mediate, in part, the influence of PTSD on SMB.

4. Develop and pilot test an integrated intervention for asthma and PTSD by adapting the Relaxation Response Resiliency Program (3RP), a mind-body program, with counseling to promote asthma SMB, and education to correct over-perception of asthma symptoms

H4: The intervention will be acceptable to WTC workers, change beliefs about asthma, correct symptom over-perception, improve asthma medication adherence and quality of life and reduce symptoms of PTSD. We are currently seeking approval for the observational portion of the study only. We will request IRB approval for the interventional (pilot) phase at a later date, in advance of commencing the pilot.

2) Background

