Sputum Inflammatory Markers: To limit participant burden, we will only perform sputum induction at the 1-month visit. However, we will have repeated measures of systemic cytokines, which will allow for longitudinal assessment of the association of PTSD-related inflammation and asthma control. During the baseline visit, we will collect data on ICS use and monitor adherence for 4 weeks. Using this information, we will be able to control for the potential effect of ICS and sputum inflammatory markers. Sputum will be collected on 175 participants (see power calculation) following standardized protocols.^{178,179} Briefly, subjects will be pre-treated with 360 µg of albuterol followed by spirometry to ensure an FEV₁ ≥60% predicted. They will then undergo a 12-minute sputum induction with PEF monitoring for participant safety. Subjects will be excluded from sputum induction if: 1) their FEV₁ <60% predicted (for safety reasons), 2) they had a respiratory tract infection <4 weeks prior to sputum induction, or 3) an asthma exacerbation or oral corticosteroid use <4 weeks prior to sputum induction. We will weight sputum samples, add a dithiothreitol (DTT) containing Sputolysin Reagent (Calbiochem, San Diego, CA, USA; 1 ml to 1 gram of sample), and then will place samples in a 37°C shaker for 15 minutes. The sample will be washed with PBS and spun down; the supernatant will be stored at -80°C.

Sputum Cell Differential: Cytospins will be prepared and stained with Diff-Quick (Dade Diagnostics of PR, Aguada, PR) for differential cell counts. The sputum cell differential will be determined by counting ~500 white blood cells on cytocentrifuge slides, excluding samples with a cell viability <50% and >20% squamous cells.^{178,180} Sputum eosinophilia will be defined as >2%;¹⁸¹⁻¹⁸³ sputum neutrophilia as ≥40%.¹⁸⁰ **Sputum Cytokines:** Sputum supernatant will be analyzed for a panel of cytokines using the multiplex assay as described above.

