All study data will be entered on a weekly basis into a computerized database. A computerized record system will be used to help the research assistants to track the follow-up interviews. To preserve participant confidentiality, study subjects will be assigned code numbers. Using these codes, none of the collection forms will contain the names or medical record number of the participants. There will be a master list matching the names of the participants to the code numbers. The list will be secured in a locked cabinet. All data will be stored on mainframe and terminals will be password protected and maintained in locked offices.

Data Analyses: We will obtain a HIPAA waiver to use de-identified data to compare non-respondents and those lost to follow-up to study participants by age, gender and ethnicity. **Descriptive Analyses:** We will use the chi-square test, t-test or Wilcoxon test to compare the baseline characteristics of WTC workers with and without PTSD. Then, we will examine the distribution of dependent variables and, as appropriate, consider transformations to reduce non-normality of continuous outcomes.

Aim 1. Assess the relationship of PTSD with systemic and airway inflammation in WTC workers and evaluate the association with asthma control: We will use the chi-square or Wilcoxon test to compare the distribution of airway inflammatory cells and systemic and sputum cytokine levels from WTC workers with and without PTSD. We will use a

 Mount Sinai	Protocol Title:	Assessing Inflammatory and Behavioral Pathways Linking PTSD to Increased Asthma Morbidity in WTC Workers
	Principal Investigator Name/Contact Info:	[name], DrPH [contact]; [contact]
	Primary Contact Name/Contact Info	[name], MS [contact]; [contact]
	Date Revised:	07/25/16
	Study Number:	IF# 1896970; GCO# 16-0945

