generalized linear model to assess the association of PTSD with sputum eosinophilia or neutrophilia (logit link), or cytokine levels (identity link) after controlling for possible confounders such as age, sex, race/ethnicity, ICS dose (calculated after adjusting for adherence), asthma onset in relation to WTC exposure, BMI, comorbidities, and depression. We will calculate the false discovery rate from the p-values to control for testing of multiple cytokines.²²³ Then, we will assess the unadjusted association of plasma and sputum cytokine levels as well as the associations of airway eosinophilia, neutrophilia, and cytokines levels with measures of asthma control using correlation coefficients or Wilcoxon test. The adjusted relationship of inflammatory markers (systemic and sputum) and asthma control measures over time will be assessed using generalized estimating equation (GEE) models (logit or identity link and autoregressive correlation structure for repeated measures over time). The model will include an interaction between inflammation markers (e.g., neutrophilia, etc.) and PTSD status to assess for potential effect modification (i.e., differential effect in subjects with vs. without PTSD). Finally, we will fit a fixed effects model (i.e. limited to within subject variability) to assess the longitudinal effect of changes in systemic cytokines levels on asthma morbidity makers.

We will use structural equation modeling (SEM; see details below) to test whether systemic inflammation, leading to airway neutrophilia and high IL-6 levels, mediates the association between PTSD and increased asthma morbidity. Following the MacArthur approach²²⁴ for assessing mediation, main effects as well as interactions between PTSD and inflammatory markers will be included as predictors of asthma morbidity.^{225,226} The analyses described above will establish if PTSD has a significant effect on the mediators (i.e., inflammatory markers), which is the first step of mediation. What is then needed is to also show that these factors are also associated with asthma morbidity measures while controlling for PTSD. Building a SEM including inflammatory markers, PTSD and an interaction variable of PTSD with the potential mediators, while controlling for other confounders, will provide a formal test of mediation.

Table 3. Power Calculations for Aim 1

Outcome	Proportion/ Mean among Participants without PTSD	Δ Proportion/ Mean for Participants with PTSD	Sample Size for 80% Power

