Sputum Neutrophilia	0.25	0.30	106
Sputum Eosinophilia	0.50	0.25	107
IL-6, pg/ml	4 (2)	2	67

 Mount Sinai	Protocol Title:	Assessing Inflammatory and Behavioral Pathways Linking PTSD to Increased Asthma Morbidity in WTC Workers
	Principal Investigator Name/Contact Info:	[name], DrPH [contact]; [contact]
	Primary Contact Name/Contact Info	[name], MS [contact]; [contact]
	Date Revised:	07/25/16
	Study Number:	IF# 1896970; GCO# 16-0945

Power Calculations: Assumptions about the expected retention rate ($\geq 80\%$), the prevalence of PTSD ($\sim 30\%$) and the distribution of inflammatory markers were derived from our preliminary data and the literature.^{1,7,8} Under these assumptions, with 175 participants undergoing sputum induction, the study will be powered to test Aim 1 hypotheses (Table 3).

Aim 2. Examine the longitudinal association between PTSD and symptom perception in WTC workers with asthma: We will calculate the proportion of blows that each participant over-estimate using AM2 data. A probit transformation will be applied to normalize the proportion of over-perceived guesses; differences in the distribution of the transformed variable at each time point in participants with and without PTSD will be assessed with a t-test.²²⁷ We will use a GEE model to assess the association between PTSD and symptom perception over time.²²⁸ We will then fit a fixed effects model (i.e., limited to within subject variability) to assess the longitudinal effect of changes in PTSD symptoms (PCL scores) on symptom perception. We will repeat these analyses adjusting for potential confounders as described above.

[figure not shown]
We will also assess the correlation between subjective (ACQ scores, use of beta2-agonists, AQLQ scores) and objective (FEV₁) measures of morbidity separately in asthmatics with and without PTSD and apply a Fisher's z' transformation to assess if the association varies between these groups. Then, we will fit a GEE model with ACQ scores (or use of beta2-agonists/AQLQ) as the dependent variable and as predictors, FEV₁, PTSD status, and an interaction between PTSD and FEV₁. In this model, the interaction term will test whether the association between objective and subjective measures varies according to the participant's PTSD status.

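### Table 3's two sputum sample sizes (106 and 107) cannot come from one calculation: at about 30% PTSD the eosinophilia row needs roughly 1.3 to 1.6 times as many participants as the neutrophilia row

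*Combined protocol and SAP*

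**What the plan says.** The power calculation for Aim 1 is in section h), under Data Analyses, in Table 3 and the paragraph below it. The last column of Table 3 is headed "Sample Size for 80% Power". The two sputum cell rows are:

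- Neutrophilia: proportion 0.25 without PTSD, change 0.30 with PTSD, sample size 106.
- "Sputum Eosinophilia": proportion 0.50 without PTSD, change 0.25 with PTSD, sample size 107.

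The paragraph begins "Assumptions about the expected retention rate" and gives retention of at least 80% and PTSD prevalence of about 30%. It concludes: "Under these assumptions, with 175 participants undergoing sputum induction, the study will be powered to test Aim 1 hypotheses (Table 3"). Section f), Sputum Inflammatory Markers, relies on the same calculation: "Sputum will be collected on 175 participants (see power calculation").

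The test appears only in the Aim 1 analysis text: "We will use the chi-square or Wilcoxon test to compare the distribution of airway inflammatory cells", followed by an adjusted model for "the association of PTSD with sputum eosinophilia or neutrophilia (logit link"). The only alpha given with any power calculation is 0.05, in the Aim 3 growth-curve paragraph.

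**The concern.** The eosinophilia row assumes a smaller difference (0.25 against 0.30), and its pooled proportion lies closer to one half, where the variance under the null is larger. It should therefore need clearly more participants than the neutrophilia row. The table asks for one more.

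The table is the stated justification for 175 sputum inductions. Read as printed, it leaves 175 − 107 = 68 spare samples for eosinophilia. A team relying on that margin could accept losses, for example to the viability and squamous-cell exclusions in section f), that this outcome may not be able to absorb.

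**Working it through.** **Inputs.** From Table 3: neutrophilia p0 = 0.25 and p1 = 0.25 + 0.30 = 0.55; eosinophilia p0 = 0.50 and p1 = 0.25 (a rise to 0.75 gives the same N by symmetry); power 80%. From the power paragraph: PTSD share f = 0.30. Assumed, because not stated: alpha 5%, two-sided first and then one-sided.

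**Formula (pooled chi-square, total N).** With d = |p1 − p0| and p̄ = f·p1 + (1 − f)·p0,

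N = [z_α·√V0 + z_β·√V1]² / d², where V0 = p̄(1 − p̄)/[f(1 − f)] and V1 = p1(1 − p1)/f + p0(1 − p0)/(1 − f).

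- Neutrophilia: p̄ = 0.340, V0 = 1.0686, V1 = 1.0929. N = (1.960 × 1.0337 + 0.8416 × 1.0454)² / 0.09 = 93.8.
- Eosinophilia: p̄ = 0.425, V0 = 1.1637, V1 = 0.9821. N = (1.960 × 1.0787 + 0.8416 × 0.9910)² / 0.0625 = 139.1.

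Neither printed figure is reproduced. Rounding each group up gives 29 + 66 = 95 and 42 + 98 = 140.

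**Other formulas** (total N, neutrophilia / eosinophilia, 30:70 split, 80% power):

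| Formula | Two-sided 5% | Ratio | One-sided 5% | Ratio |
|---|---|---|---|---|
| Pooled | 93.8 / 139.1 | 1.48 | 74.0 / 108.9 | 1.47 |
| Unpooled | 95.3 / 123.3 | 1.29 | 75.1 / 97.2 | 1.29 |
| Arcsine | 96.1 / 136.3 | 1.42 | 75.7 / 107.4 | 1.42 |
| Continuity-corrected | 109.1 / 157.6 | 1.44 | 89.1 / 127.2 | 1.43 |
| Wald log-odds | 98.0 / 152.8 | 1.56 | 77.2 / 120.3 | 1.56 |
| **Table 3** | 106 / 107 | **1.01** | | |

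Alpha and sidedness nearly cancel in the ratio, so not knowing them cannot explain the mismatch. Nor can the approximate prevalence: for a PTSD share of 25% to 35% the ratio is 1.26 to 1.60, and for any share from 5% to 95% it stays at or above 1.08.

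**Matching each row alone.** A two-sided 5% Fisher exact test gives 81.5% power for neutrophilia at 106 (32 vs 74) but 63.4% for eosinophilia at 107 (32 vs 75). A one-sided 5% pooled test gives 79.4% for eosinophilia at 107 but 90.8% for neutrophilia at 106. The two rows look right only under different conventions.

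**Alternative reading.** If 0.30 were the proportion in the PTSD group rather than the change, 0.25 vs 0.30 would need about 2,950. The column header also marks the value as a difference.

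**Power at the relevant sizes** (pooled, two-sided 5%). Power = Φ[(d√N − z_α√V0)/√V1]. For eosinophilia at 107: (0.25 × 10.344 − 2.114)/0.991 = 0.476, so 68.3%.

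| N | Neutrophilia | Eosinophilia |
|---|---|---|
| 106 (neutrophilia) / 107 (eosinophilia) | 84.5% | 68.3% |
| 140 (= 175 × 0.80) | 92.8% | 80.3% |
| 175 | 96.8% | 88.6% |

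Other two-sided 5% methods give eosinophilia power at 107 of 60% (continuity-corrected, exact enumeration), 63% (Fisher), 65% (Wald log-odds), 70% (chi-square, exact enumeration) and 74% (unpooled). None reaches 80%.

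**The case against.** The strongest reply is that no decision changes. The conclusion about 175 refers to the Aim 1 hypotheses, and none of H1a to H1c names eosinophilia. H1b says "WTC workers with asthma and PTSD will have an increased expression of sputum neutrophilia and IL-6 levels", and neutrophilia is well powered at 140 or 175. This stands, and it limits the finding to the table. Eosinophilia nevertheless remains a planned Aim 1 outcome with its own row, and that row is part of the stated basis for the inductions.

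A second reply is that the eosinophilia figure need not be the wrong one. With a one-sided 5% test, 107 is about right (107.4 arcsine, 108.9 pooled) and 106 is merely generous. This also stands: the documents do not show which convention either row used. The figure of 140 depends on a two-sided 5% chi-square test, which the analysis text makes reasonable but the power text does not state. The inconsistency between the rows does not depend on that choice.

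A third point is that 175 is not comfortable under every test. The continuity-corrected total is 48 + 111 = 159; if 80% retention applies, 159/0.80 is about 199. At 140, Fisher power for eosinophilia is 78.1%. If all 175 samples are analysed, 159 is covered.

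Finally, the IL-6 row might properly use a stricter alpha, because the plan controls the false discovery rate across cytokines. That is possible but undocumented, and is a reason to state any such difference for that row.

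**Conclusion.** The concern holds. At about 30% PTSD, 106 and 107 cannot both be sample sizes for 80% power under one convention: the ratio should be about 1.3 to 1.6 and is 1.01. Under a two-sided 5% chi-square test the eosinophilia figure is 33 too low (140 against 107), and 107 gives 68% power. The apparent margin of 68 samples becomes 175 − 140 = 35, and is used up exactly if 80% retention applies, since 140/0.80 = 175. Whether retention applies to a single induction at month 1 is not stated.

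This is a misstated table and safety margin, not an underpowered hypothesis. The 175 inductions remain adequate for neutrophilia. They are adequate for eosinophilia with the uncorrected chi-square test at either 140 or 175, or with the continuity-corrected test if all 175 are analysed.

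**What to change.** Under Table 3, state the alpha, sidedness, test, 30:70 split, direction of each change, and whether the 80% retention applies to the sputum sample. Recompute the rows on that convention.

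With a two-sided 5% chi-square test, the entries become 95 for neutrophilia (29 + 66; 110 with continuity correction) and 140 for eosinophilia (42 + 98; 159 with correction). Give eosinophilia power as about 89% with 175 analysed and about 80% with 140.

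In the IL-6 row, say what the value 2 in parentheses is and recheck 67. If it is a standard deviation, 67 gives about 96% power at two-sided 5%, so the row also does not correspond to 80% on that convention. If a stricter alpha was intended for cytokines, say so.

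The cost is one corrected table and a sentence or two. With the uncorrected two-sided test, neither enrolment nor the 175 inductions change.

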For the observational phase of the study, sources of data will be the interviewer-administered surveys, the WTCHP database, spirometry, airway and peripheral blood samples, the AM2 device, electronic

 Mount Sinai	Protocol Title:	Assessing Inflammatory and Behavioral Pathways Linking PTSD to Increased Asthma Morbidity in WTC Workers
	Principal Investigator Name/Contact Info:	[name], DrPH [contact]; [contact]
	Primary Contact Name/Contact Info	[name], MS [contact]; [contact]
	Date Revised:	07/25/16
	Study Number:	IF# 1896970; GCO# 16-0945

adherence monitors, and the electronic medical record (EMR). Interviews will be conducted in English or Spanish in person (as required for several measures) at baseline, 1, 6, and 12 months (See Table below).

Summary of Measures and Timing of Data Collection

Variables	Instrument(s) or Measure(s)	Source	Timing of Collection (Month)					
			0	1	6	12		
OUTCOMES								
Inflammatory Markers								
Sputum Cell Differential	Sputum induction/cytospins	Sputum		✓				
Sputum Cytokines	Multiplex assays of sputum supernatant	Sputum		✓				
Systemic Cytokines	Multiplex assays	Plasma	✓	✓	✓	✓		
Symptoms Perception								
Symptom Perception	AM2 electronic devices		✓	✓	✓	✓		
Self-management								
Objective Adherence	Smartinhaier, Smart disk		✓	✓	✓	✓		
Self-reported Adherence	Medication Adherence Report Scale	Horne ¹⁸⁰	✓	✓	✓	✓		
Other Behaviors	Inhaler technique, trigger avoidance, etc.	Van Beerendonk ¹⁹⁰	✓	✓	✓	✓		
Asthma Morbidity								
Airway Obstruction	Forced expiratory volume at 1 second/PEF	Spirometry/AM2	✓	✓	✓	✓		
Asthma Control	Asthma Control Questionnaire	Juniper ¹⁹⁷	✓	✓	✓	✓		
Use of Beta- ₂ Agonists	Doser electronic devices		✓	✓	✓	✓		
Resource Utilization	Emergency Department use, Hospitalizations	EHR/self-report	✓	✓	✓	✓		
Quality of Life	Asthma Quality of Life Questionnaire	Juniper ²¹⁰	✓	✓	✓	✓		
PREDICTORS								
PTSD	SCID, PTSD Checklist	First ²⁰⁰	✓	✓	✓	✓		
Asthma Health Beliefs	Asthma-Illness Perception Questionnaire	Weinman ²¹¹	✓	✓	✓	✓		
Asthma Medication Beliefs	Beliefs about Medications Questionnaire	Horne ¹³⁰	✓	✓	✓	✓		
Anxiety Sensitivity	Anxiety Sensitivity Index 3	Taylor ²⁰⁹						
Asthma History	Age of onset, intubations, asthma regimen, etc.		✓					
Medication Regimen	Chart review and self-report		✓	✓	✓	✓		
Comorbidities	Charlson Index	Charlson ²¹²	✓					
Depression	SCID/PHQ-9	Spitzer ²⁰⁴	✓		✓	✓		
WTC exposures	Exposures at the WTC site, protection	WTCHP survey	✓					

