Covariates: Asthma History: Items about asthma history will include: age of onset and relation to 9/11, oral steroid use, history of intubation, and past ED visits and hospitalizations. We will obtain detailed information regarding onset of symptoms in relation to WTC-related exposure and whether symptoms or medication requirements worsened after WTC work among workers with preexisting asthma (WTC-exacerbated asthma).⁴ Individuals with onset of asthma symptoms shortly after 9/11 exposures (no latency), will be categorized as having irritant-induced asthma. Patients with insidious onset of asthma symptoms within 1-2 years of exposure will be classified as having late onset asthma, possible irritant-induced;⁴ those with asthma onset >2 years post exposure will be coded as having late onset asthma, probably not irritant-induced. At each visit, we will determine participants' asthma medications and their dosages by self-report and by querying the EMR. The concentration of total and allergen-specific (house dust mites, molds, cockroaches, cats, and mice) IgE will be used to assess sensitization to key indoor allergens in peripheral blood.²¹⁴⁻²¹⁶ Information on home environmental exposures will be obtained from validated questionnaires.^{217,218} We will also collect data on asthma symptoms in relation to current job and environmental triggers encountered in the current workplace.

Medical Comorbidities: History of physician diagnosis of sinusitis, rhinitis, GERD, and OSA will be assessed using questions from the WTCHP survey.²¹⁹ Body mass index will be assessed using height and weight data collected during spirometry. We will use Charlson's Index to assess the workers' burden of comorbidities.²¹² Smoking and Alcohol Use: will be measured with items from the National Health Interview Survey (NHIS).²²⁰

WTC-Related Exposures: We will use data collected as part of the WTCHP to characterize WTC exposures of study participants. Variables include time of arrival, exposure to the dust cloud, work location, total duration of exposure, and type of activities performed. Exposure will be categorized in four levels based on the total time a responder spent working at the WTC site, exposure to the cloud of debris, and work on the pile of debris.¹ We will also assess for psychological stressors including shift length, exposure to body parts, and fear for personal safety. Use of respiratory protection will be assessed with data collected as part of WTCHP survey.

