Power Calculations: We estimated rates of over-perception and asthma morbidity from our prior studies or the literature.^{27,109,154,155,168,229} We adjusted the sample size for the expected correlation of measurements within a participant (interclass correlation coefficient ≥ 0.8).²³⁰ These analyses showed that with 400 patients, the study will have $>90\%$ power to detect a 10% increase in the probability of over-perception in participants with PTSD. We also evaluated the power to identify whether the regression coefficients for the association between the ACQ/AQLQ scores and FEV₁ is different for patients with vs. without PTSD (equivalent to testing an interaction). These analyses showed that with 400 subjects (and 80% retention), the study will have an 82% power to detect a difference of 1 unit between the slopes of patients with and without PTSD.

Aim 3. Assess the relationship between PTSD and adherence to asthma SMB in WTC workers and identify the pathways linking them: Medication adherence analyses will be restricted to patients prescribed controller medications ($>80\%$ of the sample based on prior studies). Primary analyses will use electronic adherence measures; secondary analyses will use MARS scores and other SMB. The univariate association of adherence and PTSD will be assessed using a chi-square test. Multivariable analyses will use a GEE model (logit link function) to control for potential confounders as listed above. We will use similar approaches to assess the associations of potential mediators (over-perception of symptoms, anxiety sensitivity, and illness and medication beliefs, Figure 5) of the relationship between PTSD and medication adherence.

 Mount Sinai	Protocol Title:	Assessing Inflammatory and Behavioral Pathways Linking PTSD to Increased Asthma Morbidity in WTC Workers
	Principal Investigator Name/Contact Info:	[name], DrPH [contact]; [contact]
	Primary Contact Name/Contact Info	[name], MS [contact]; [contact]
	Date Revised:	07/25/16
	Study Number:	IF# 1896970; GCO# 16-0945

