Latent Growth Curve Modeling (LGCM): We will employ LGCM approaches to test the mediation model presented in Figure 5.^{231,232} The analysis will involve longitudinal assessment of asthma SMB across 3 time points (0, 6, and 12 months). We hypothesize that both time-varying covariates (e.g., illness and medication beliefs) and time-invariant covariates (e.g., age, sex, etc.) will predict asthma SMB assessed at these time points. We also hypothesize potential lagged effects of covariates at earlier time points. As a first step, we will identify the measurement model for the latent variables using confirmatory factor analysis. Specifically, we will create latent variables representing random effects intercepts and slopes for illness and medication beliefs (IB_{t0} , IB_{t6} , and IB_{t12} ; where $t0$ represents baseline illness beliefs scores), anxiety sensitivity and asthma SMB measures. Illness representations will be measured by 5 independent factors (i.e., identity, timeline, etc.), medication representations by 2 factors (i.e., necessity and concerns), and anxiety sensitivity by 3 factors. Emotional representations will be modeled as a single domain. This approach will allow us to test specific pathways. This model will also include the control variables listed above. We will estimate slope and intercept parameters using a Weighted Least Squares Mean-Variance adjusted (WLSMV) estimator, which provides robust estimates for complex models with modest sample sizes. We will test this measurement model for absolute fit using Chi-square and RMSEA statistics.^{232,233}

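### Read literally, the Aim 3 adherence model adjusts for an ICS dose that is itself computed from adherence

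*Combined protocol and SAP*

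**What the plan says.** All of this is in the combined protocol and SAP, mostly under section h), Data Analyses.

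- **Aim 3, adjustment.** "Multivariable analyses will use a GEE model (logit link function) to control for potential confounders as listed above". No list follows.
- **Aim 3, outcome.** "Primary analyses will use electronic adherence measures; secondary analyses will use MARS scores and other SMB". Under Asthma Controller Medication Adherence, the electronic measure is monitored ICS use for 4 weeks after each interview. A participant is adherent if the drug is used on at least 70% of prescribed days.
- **Aim 1, the list.** The inflammation models are fitted "after controlling for possible confounders such as age, sex, race/ethnicity, ICS dose (calculated after adjusting for adherence"), followed by asthma onset relative to WTC exposure, BMI, comorbidities and depression.
- **Aim 2.** This only points back: "We will repeat these analyses adjusting for potential confounders as described above".
- **Latent growth curve model (LGCM).** "This model will also include the control variables listed above".
- **Why the adjusted dose exists.** Under Sputum Inflammatory Markers, ICS use and 4 weeks of monitored adherence are collected so that ICS effects can be controlled in the sputum analyses.
- **Unadjusted dose.** The Medication Regimen row of the measures table (source: "Chart review and self-report") is ticked at every visit. The Covariates text records "asthma medications and their dosages by self-report and by querying the EMR".

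**The concern.** Adherence-adjusted dose is sensible in Aim 1, where it stands for the drug actually taken and the outcome is airway or systemic inflammation. In Aim 3 the outcome is whether that same drug was taken. There the covariate is a function of prescribed dose and the outcome, so adjusting for it is over-adjustment and does not control confounding.

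The adjusted GEE is the multivariable test of H3a on the primary adherence measure. The covariate could shrink a real PTSD effect, leave it unchanged by coincidence, inflate it, or create an association where none exists. Which of these happens depends on how prescribed dose differs by PTSD status, and the documents do not say. Higher doses with PTSD are plausible, because the Background reports worse asthma control in that group, but this is not documented.

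**Working it through.** The plan states no power or effect size for the H3a model, so there is no figure of its own to reproduce. The check has three steps.

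**1. Trace the pointers.** The Aim 3 GEE refers to confounders listed above. Aim 2, immediately before it, gives no list and refers further back. Aim 1 has the only list labelled confounders, and it contains the adherence-adjusted dose. No later sentence excludes it.

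**2. Sign of the bias, as a linear approximation on the log scale.** Let P be PTSD, log adherence A = bP + e, and log prescribed dose D = cP + u. The adjusted dose is S = A + D = (b + c)P + e + u. In a regression of A on P and S, the coefficient of S is L = var(e) / (var(e) + var(u)). This is the share of adjusted-dose variance, within PTSD groups, that comes from adherence. The PTSD coefficient becomes b - L(b + c), so

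bias = -L(b + c).

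With b < 0, as H3a expects:

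- c = 0: bias = -Lb > 0, toward the null.
- c = -b: no bias, because the two parts cancel.
- c > -b: bias is negative, away from the null.
- c < 0: toward the null, and past it when L|c| > (1 - L)|b|.

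With b = 0 the bias is -Lc. This is zero if dose is unrelated to PTSD; otherwise a spurious association appears. L is large when prescribed doses vary little. In the limit of one common dose and a covariate updated at each visit, the covariate determines the outcome completely.

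**3. Size, by simulation.**

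*From the documents:*

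- PTSD prevalence 30%.
- About 50% adherent overall, set at 55% without PTSD.
- The 70% rule applied to 28 days, giving 20 or more days.
- Visits at 0, 6 and 12 months, as in the LGCM text.
- n = 400 x 0.80 on controllers x 0.80 retained = 256.

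*Assumed:*

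- Person SD of logit daily use 1.0 or 1.5, and visit SD 0.5.
- Prescribed-dose log-SD 0.3, 0.5 or 0.8.
- Adjusted dose = dose x share of days used.
- Working independence, since Aim 3 names no correlation structure.

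The plan gives no formula for the adjusted dose. It also does not say whether the dose is fixed from the 4 weeks after baseline or updated after each interview, so both were run. Large-sample PTSD odds ratios (300,000 persons x 3 visits per setting):

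| True OR | Prescribed dose with PTSD | Fixed at baseline | Updated each visit |
|---|---|---|---|
| 0.50 | unrelated | 0.52-0.64 | 0.52-0.64 |
| 0.50 | 5% more | 0.51-0.54 | 0.49-0.52 |
| 0.50 | 10% more | 0.46-0.50 | 0.40-0.49 |
| 0.50 | 22% more | 0.33-0.47 | 0.24-0.45 |
| 0.50 | 18% less | 0.56-1.18 | 0.59-1.56 |
| 1.0 | unrelated | 1.00 | 1.00 |
| 1.0 | 10% more | 0.73-0.95 | 0.63-0.94 |
| 1.0 | 22% more | 0.51-0.91 | 0.38-0.88 |

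Ranges run over the assumed SDs; the mildest values come with wide dose spread. At a true OR of 0.50 the biases cancel at a dose excess of 7-10% (fixed) or 5-8% (updated). With prescribed dose as the covariate, the fits gave 0.496-0.498 and 0.995-0.997. Entering the adjusted dose on a log scale gave the same pattern.

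At n = 256 (2000 replicates per setting, sandwich standard errors, two-sided 0.05):

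| Quantity | Dose with PTSD | Fixed | Updated | Prescribed dose as covariate |
|---|---|---|---|---|
| Power, OR 0.50 | unrelated | 0.38-0.82 | 0.29-0.80 | 0.80-0.87 |
| Power, OR 0.50 | 10% more | 0.78-0.89 | 0.76-0.88 | not tabulated |
| False positives, OR 1.0 | unrelated | about 0.05 | about 0.05 | 0.04-0.06 (all settings) |
| False positives, OR 1.0 | 10% more | 0.05-0.21 | 0.05-0.30 | as above |
| False positives, OR 1.0 | 22% more | 0.07-0.68 | 0.09-0.83 | as above |

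**The case against.** The strongest reply is that this is one reading of a loose pointer. The Aim 1 list is open (it says such as) and was written for other outcomes. A variable built from the outcome is not a confounder, so a careful analyst would drop it. The Covariates text is the protocol's own covariate section and holds unadjusted dosages, and the LGCM text mentions "time-invariant covariates (e.g., age, sex, etc".) without any dose. All of that is fair, and it means nobody can say the fitted model will contain the item. But none of those places is called a confounder list and none excludes the adjusted dose. Dropping it would be a decision the plan does not record.

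Other limits also stand:

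- If the dose is fixed at baseline, only the baseline outcome shares its data. At 6 and 12 months the model then adjusts for earlier adherence, which PTSD may already have affected. That is a different problem, but still not confounder control.
- The extreme values need a narrow dose spread together with a PTSD-dose difference that is undocumented. With wide spread and no dose difference, 0.50 moves only to about 0.52.
- n = 256 is a floor: the plan expects more than 80% on controllers and at least 80% retention, and GEE can use participants who leave later.
- The measures table also ticks objective adherence at month 1, which was not simulated.
- The unadjusted chi-square test is unaffected, and inhaler technique and trigger avoidance are not components of the adjusted dose.
- The LGCM bias was not quantified, and its Figure 5 is not available here.

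**Conclusion.** The concern holds as a defect of the written rule: followed literally, the adjusted test of H3a on electronic adherence conditions on a variable computed from adherence. Neither the direction nor the size of the bias can be fixed from the documents, because they give neither the spread of prescribed doses nor their relation to PTSD. Under the assumptions above, the distortion runs from negligible (wide dose spread, or a dose excess near the cancelling point) to a reversed sign or a badly inflated false-positive rate. These figures illustrate the range; they are not estimates for this cohort. Prescribed dose as the covariate showed no such bias in any setting. The LGCM inherits the same ambiguity through its own pointer, and nothing stronger is claimed for it.

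**What to change.** Give Aim 3 its own confounder list. State that the adherence-adjusted ICS dose is excluded from every model with adherence as the outcome, both GEE and LGCM. If a dose term is wanted, name the prescribed ICS dose or regimen already recorded at each visit. Keep the adherence-adjusted dose in the Aim 1 inflammation models, and state there how it is calculated and from which monitoring period. The cost is one or two sentences in the analysis plan, with no new data.
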